H0 – Bonding to NCCLs with FBDC-SE (G1) and MM-SE(G4G6) result in similar restorations (aesthetic, functional and biologic) success rates;

H0 – Bonding to NCCLs with FBDC-SE (G1) and MM-SE (G4G6) adhesives result in similar restoration retention rates;

H0 – Bonding to NCCLs with FBDC by SE and enamel etching mode (FBDC-SE-EE; G2) and MM adhesives by Etch-and-Rinse mode (MM-ER; G3G5) result in similar (no significant differences) clinical (aesthetic, functional and biologic) behaviour/performance;

H0 – Bonding to NCCLs with FBDC-SE-EE (G2) and MM-ER (G3G5) result in similar restorations (aesthetic, functional and biologic) success rates;

H0 – Bonding to NCCLs with FBDC-SE-EE (G2) and MM-ER (G3G5) result in similar restoration retention rates;

H0 – Bonding to NCCLs with FBDC (G1G2) or FBU (G3G4), DC adhesives, and ADU (G5G6) light-curing adhesive, with SE or SE-ER/ER modes result in similar (no significant differences) clinical (aesthetic, functional and biologic) behaviour/performance;

H0 – Bonding to NCCLs with FBDC (G1G2) or FBU (G3G4) and ADU (G5G6) lightcuring adhesive, with SE or SE-ER/ER modes result in similar restorations (aesthetic, functional and biologic) success rates;

H0 – Bonding to NCCLs with FBDC (G1G2) or FBU (G3G4) and ADU (G5G6) lightcuring adhesive, with SE or SE-ER/ER modes result in similar restoration retention rates;

H0 - FDI or USPHS criteria evaluation outcomes not differ for the same data, at 24th month follow-up.

2 – POPULATION, MATERIALS AND METHODS

2.1- TRIAL DESIGN

The trial design follows the Consolidated Standards of Reporting Trials (CONSORT) statement (30). Prospective, double blind, clinical trial; randomized allocation of NCCL restorations by six adhesion interventional groups (6 arms) for examination of restorations performance.

Study will take place in University

Dentistry School Clinic. Participants recruitment between November 2015 and April 2016. Restorations estimated to be done until April or May 2016 year.

-

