Study variable definition_- Clinical/direct observation and performance evaluation acceptance by means of FDI (*FDI World Dental Federation - clinical criteria for the evaluation of direct restorations*) (Adapted from (33) (Annex 3) and USPHS (34) (Annex 4).

2.7- DATA AND STATISTICAL ANALISYS PLAN (SAP)

Data statistical analysis and description according to aims of this trial; Specific program for statistical data analysis (IBM(c) SPSS(c) Statistics vs. 22 or later) will be used. The changes in parameters clinical performance (paired comparison analysis) by both, FDI and USPHS criteria will be assessed by McNemar or Wilcoxon tests, for both

primary and secondary outcomes, to determine differences between treatments with regard to aesthetic, functional and biological parameters from baseline to 24th month recall (longitudinal assessment). Differences will be considered to be significant at P<0.05. Whenever 3 groups will be compared at 24 months' recall, a Kruskal Wallis test will be used and upon significant differences detection, then Mann-Whitney tests considering Bonferroni correction will be used for pairwise group comparisons.

Comparison of FDI and USPHS acceptance (success rate) criteria evaluation outcomes for Esthetic, for Functional and for Biological Parameters, at 24th Month Follow-up, were compared using the chi-square test.

If missing data occurs, that is, if dropouts or non-observed due to loss of retention of the restoration, then the paired comparison will consider for the baseline just the restorations existing at the last moment (24 months).

2.8- OBSERVATIONS REGARDING SAMPLE CALCULATION

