It was assumed that the minimum number of adhesive restorations to be held in each of the six arms (G1 to G6) is 35 (210 restorations). The researchers did not have detailed information that allows the estimation of the sample size based on power analysis (the effect of the expected difference to the end of the time considered for the study). Thus, in principle they assumed the rules of thumb, usually considered in research situations where there is no advance information concerning the performance evaluation of these adhesive medical devices available on the market, using this assay. Moreover, when considering a "simple" analysis comparison using a McNemar test (repeated measures) in six groups would be necessary in total, including at least 80 cases (to restore teeth) in the sample. When considering at least 35 restorations by group, researchers are greatly increasing the minimum number stipulated in the aforementioned technique. In addition, clinical studies previously performed on this issue (between 2004 and 2012) relative to the post-market clinical evaluation performance of adhesive products/use mode in NCCLs, in the context of restorative dentistry field, has enabled to measure a minimum of 30 restorations as viable for determining events in a short/mean-term as the clinical performance evaluation of a similar nature of adhesives.

2.9- GOOD CLINICAL PRACTICE FOR CLINICAL RESEARCH

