ANNEX 3 WORLD DENTAL FEDERATION (FDI) CRITERIA

A) ESTHETIC PROPERTIES	1. Surface Luster	2. Staining margin	3. Colour stability and translucency
1. Clinically excellent/ very good	1.1 Luster comparable to enamel	2.1 No surface staining	3.1 Good colour match no diference in shade and translucency.
2. Clinically good (after correction, very good)	1.2 Slightly dull, not noticeable from speaking distance.	2.2 Minor staining, easily removable.	3.2 Minor deviations
3. Clinically sufficient/ satisfactory (minor shortcomings with no adverse effects but not adjustable without damage to the tooth)	1.3 Dull surface but acceptable if covered with film of saliva.	2.3.Moderate surface staining, also present on other teeth, not aesthetically unaccetable.	 3.3 Clear deviation but acceptable. Does not affect aesthetics: 3.3.1.more opaque 3.3.2.more translucent 3.3.3 darker 3.3.4 brighter
4. Clinically unsatisfactory (repair for prophylactic reasons)	1.4 Rough surface, cannot be masked by saliva film, simple polishing is not sufficient. Further intervention necessary.	2.4 Surface staining present on the restoration and is unacceptable; major intervention necessary for improvement	 3.4 (Localised) clinically unsatisfactory but can be corrected by repair 3.4.1 too opaque 3.4.2 too translucent 3.4.3 too dark 3.4.4 too bright
5. Clinically poor (replacement necessary)	1.5. Quite rough, unacceptable plaque retentive surface.	2.5 Severe staining and/or subsurface staining (generalized or localized); not accessible for intervention	3.5 Unacceptable. Replacement necessary.
Acceptable or not acceptable (n, %, and reaso Adapted from (33)	ns)		

B) FUNCTIONAL PROPERTIES	4. Fractures and Retention	5. Marginal Adaptation
1. Clinically excellent/ very good	4.1Restoration retained, no	5.1
	fractures/cracks.	Harmonious outline, no gaps, no
		discoloration.
2. Clinically good (after correction,	4.2. Small hairline crack	5.2.1 Marginal gap (50 μm)
very good)		5.2.2 Small marginal fracture removable by
		polishing.
3. Clinically sufficient/ satisfactory	4.3. Two or more or larger hairline cracks	5.3.1
(minor shortcomings with no adverse	and/or chipping(not affecting the	Gap<150 µm not removable
effects but not adjustable without	marginal integrity or proximal contact.	5.3.2
damage to the tooth)		Severe small enamel or dentin fractures
4. Clinically unsatisfactory (repair	4.4	5.4.1
for prophylactic reasons)	Chipping fractures which damage	Gap> 250 µm or dentine exposed

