	marginal quality or proximal contacts;	5.4.2
	bulk fractures with or without partial	Chip fracture damaging margins
	loss(less than half of the restoration)	5.4.3
		Notable enamel or dentine wall fracture
5. Clinically poor (replacement	4.5. Parcial or complete loss of restoration	5.5
necessary)		Filling is loose but in situ.
Acceptable or not acceptable (n, %, and reasons)	
Adapted from (33)		

c) BIOLOGICAL PROPERTIES	6. Postoperative Hipersesibility, tooth vitality	7. Recurrence of Caries, erosion, abfraction	8. Tooth integrity (enamel cracks)
1. Clinically excellent/ very good	6.1 No hipersensitivity, normal vitality	7.1 No secondary or primary caries	8.1 Complete integrity.
2. Clinically good (after correction, very good)	6.2 Low hipersensitivity for a limited period of time, normal vitality.	7.2 Very small and localized1. Demineralization2. Erosion or3. Abfraction.No operative treatmentrequired	8.2.1 Small margin enamel(<150 μm) 13.2.2 Hairline crack in enamel (<150 μm not probable)
3. Clinically sufficient/ satisfactory (minor shortcomings with no adverse effects but not adjustable without damage to the tooth)	 6.3.1 Premature/slightly more intense 6.3.2 Delayed/weak sensitivity; no subjective complaints, no treatment needed. 	 7.3.Larger areas of 1.Desmineralisation 2.Erosion 3. Abrasion/abfraction in dentine Localized and acessible and can be repaired 	8.3.1 Enamel split(<250 μm) 8.3.2 Crack < 250 μm, no adverse effects.
4. Clinically unsatisfactory (repair for prophylactic reasons)	6.4.1 Premature/very intense 6.4.2 Extremely delayed/weak with subjective complaints 6.4.3 Negative sensitivity intervention necessary but not replacement	7.4.1Caries with cavitation 7.4.2 Erosion in dentine 7.4.3 Abrasion/abfraction in dentine Localized and accessible and can be repaired	 8.4.1 Major enamel split (gap>250 μm or dentine or base exposed) 8.4.2 Crack>250 μm (probe penetrates).
5. Clinically poor (replacement necessary) Acceptable or not acceptable (n, %, and read	6.5 Very intense, acute pulpitis or no vital.Endodontic treatment is necessary and restoration has to be replaced.	7.5 Deep secondary caries or exposed dentine that is not accessible for repair of restoration.	8.5 Cusp or tooth fracture.
Acceptable or not acceptable (n, %, and rea Adapted from (33)	(SUIIS)		

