ANNEX 4 USPHS (MODIFIED U.S. PUBLIC HEALTH SERVICE) CRITERIA Used for Clinical Evaluation

PARAMETER	CRITERIA	RYGE SCORE*			
ESTHETICS	Surface Staining	Alfa (α): No staining in the restoration and/or the tooth			
Lonnes	Surface Stanning				
		Bravo (B): Slight staining in the restoration and/or the tooth			
		Charlie (χ): The staining penetrated in the restoration and/or the tooth			
	N	in a pulpar direction			
	Marginal	Alfa (α): No discoloration along the margin between the restoration an			
	Discoloration	adjacent tooth			
		Bravo (3): Slight discoloration along the margin between the restoration			
		and the adjacent tooth (removable, usually localized)			
		Charlie (χ): Deep staining cannot be polished away			
	Color Match	Alfa (α)*: Restoration matches the adjacent tooth structure in color and			
		translucency			
		Bravo (3)*: Light mismatch in color, shade or translucency between th			
		restoration and the adjacent tooth			
		Charlie $(\chi)^*$: The mismatch in color and translucency is outside the			
		acceptable range of tooth color and translucency			
FUNCTIONAL	Retention	Alfa (a): Retained			
		Bravo (B): Partially retained			
		Charlie (χ): Missing			
	Marginal Integrity	Alfa (α): No visible evidence of crevice along the margin			
	(Adaptation)	Bravo (B): Visible evidence of a crevice along the margin into which			
		the explorer will penetrate			
		Charlie (χ): Dentin or the base is exposed			
		Delta (δ)*: Restoration is fractured, mobile or missing			
BIOLOGICAL	Postoperative	A: No evidence of postoperative sensitivity			
	Sensitivity	B: Experience of postoperative sensitivity			
	Secondary Caries	A*: No evidence of caries			
		B*: Evidence of caries along the margin of the restoration			
	Gingival Bleeding	A: No evidence of gingival bleeding adjacent to Class II restoration			
		B: Evidence of gingival bleeding adjacent to Class II restoration			
*Alfa (α): Clin	ically excellent/ verv	good; highest degree of clinical acceptance. Bravo (B): Clinical			

present. B: Presence of pathology, related to restoration.

[†]Source: Adapted from (34)

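### In the Esthetic and Biological domains, the planned FDI–USPHS comparison mixes how each scale judges with what each scale covers

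*Combined protocol and SAP*

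**What the plan says.** The last null hypothesis under Objectives and Hypothesis is "FDI or USPHS criteria evaluation outcomes not differ for the same data, at 24th month follow-up". Section 2.7 gives its test: "Comparison of FDI and USPHS acceptance (success rate) criteria evaluation outcomes for Esthetic, for Functional and for Biological Parameters", at 24 months, "were compared using the chi-square test". The general threshold in 2.7 is "Differences will be considered to be significant at P<0.05". Section 2.8 sets the size: "the minimum number of adhesive restorations to be held in each of the six arms (G1 to G6) is 35 (210 restorations".

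Section 2.6 has the three examiners score every restoration on both scales at each recall. Annex 3 prints one acceptable-or-not line under each of its three domain tables, and Annex 4 lists the same three domains in its parameter column. The comparison therefore reads as one of domain acceptance.

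The FDI list contains "1. Surface Luster" and "8. Tooth integrity (enamel cracks"). The USPHS list contains an item graded on "evidence of gingival bleeding adjacent to Class II restoration". Nothing in section 2.7 or the annexes maps items from one scale to the other, limits the comparison to matched items, or legibly states how item grades combine into domain acceptance.

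**The concern.** The hypothesis speaks of the same data, which suggests two scales judging the same features. In two domains the scales are partly looking at different features. If gums bleed around otherwise sound restorations, USPHS biological acceptance can fall while FDI acceptance stays put, even though the scales agree on everything they both measure. Enamel cracks can do the reverse.

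A significant result could then be read as the scales differing in judgement when only their coverage differs. Unmatched items failing at similar rates on the two scales could also offset each other, so that a non-significant result conceals many restorations on which the two verdicts differ. Either way, the test of this hypothesis is hard to interpret.

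**Working it through.** **Item lists side by side** (Annexes 2, 3 and 4)

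| Domain | On both scales | FDI only | USPHS only |
|---|---|---|---|
| Esthetic | surface staining; colour | luster | marginal discoloration |
| Functional | retention/fracture; marginal adaptation | none | none |
| Biological | sensitivity; caries | tooth integrity | gingival bleeding |

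Three details matter for the matching.
- FDI item 2 is headed as marginal staining in Annex 3 and as surface staining in Annex 2. Its grades describe surface staining.
- FDI items 4, 6 and 7 also cover fracture, tooth vitality, and erosion/abfraction. USPHS places fracture in the Delta grade of marginal integrity.
- FDI grade 5.1 mentions absence of discoloration, but in the Functional domain and only in the top grade.

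**Inputs.** The plan states no figure for this comparison, so there is none to reproduce; its total checks, 6 × 35 = 210. The threshold is 0.05, and section 2.7 does not mention a continuity correction. All failure rates below are assumptions, because the documents give none. Two scoring assumptions are also needed: one failed item fails the domain, and a bleeding grade B is unacceptable.

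**Formula.** With a failures on FDI and b on USPHS, each out of n, and pooled p̄ = (a + b)/(2n):

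X² = ((b − a)/n)² / [p̄(1 − p̄) × 2/n]

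**No failures on shared items, k restorations failing on bleeding alone, n = 210** (a = 0, b = k)
- k = 3: X² = 0.00020408 / 0.00006754 = 3.02, below the critical value 3.84.
- k = 4 (1.9%): X² = 0.00036281 / 0.00008984 = 4.04, p = 0.0445.
- With Yates correction or Fisher's test, k = 6 is needed (p = 0.040 and 0.030).
- Exact McNemar with all k discordant pairs in one direction has p = 2 × 0.5^k. This is 0.0625 at k = 5 and 0.031 at k = 6 (2.9%).

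With an assumed 20% loss (n = 168), the counts stay at 4 for Pearson (p = 0.044) and 6 for McNemar. A paired test alone therefore does not remove the problem.

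**Some failures on shared items.** If 10 of 210 fail a shared item on both scales, Pearson needs k = 11 (10 against 21 failures, p = 0.040); McNemar still needs 6. Put as rates, with 200 of 210 acceptable on FDI and bleeding independent of the other items, USPHS acceptance is about 0.95 × (1 − g):

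| Bleeding rate g (assumed) | Acceptable on USPHS | Pearson p |
|---|---|---|
| 5% | 190/210 | 0.058 |
| 10% | 180/210 | 0.0009 |
| 20% | 160/210 | 2.4 × 10⁻⁸ |

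**Simulated rejection** (10,000 runs, n = 210, full agreement on shared items)

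| Shared failures | USPHS-only failures | Chi-square | Exact McNemar |
|---|---|---|---|
| 0 | 2% | 61% | 24% |
| 0 | 5% | 99% | 96% |
| 5% | 2% | 0.5% | 22% |
| 5% | 5% | 42% | 94% |

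**Offsetting.** With no shared failures and unmatched items failing independently at 5% on each scale, the verdicts differ on 2 × 0.05 × 0.95 = 9.5% of restorations, about 20 of 210. Chi-square rejects in only 4.7% of runs.

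**After restriction to matched items.** With full agreement on them, discordance is zero and neither test rejects in any run.

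**The case against.** The strongest reply is that the hypothesis may concern whole instruments: does the choice of scale change the reported success rate? On that reading, coverage is part of the instrument and a coverage-driven difference is a correct rejection. The text allows this, so the domain comparison is not wrong in itself. But the plan does not say that this is the question. The Introduction cites an 18-month trial in which modes differed on marginal adaptation by FDI but not by USPHS, which is a contrast on a shared item.

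The figures also depend on scoring rules that the plan does not legibly give. This stands, and the figures are conditional on them. Annex 4 describes a biological B as pathology related to the restoration, which makes an unacceptable reading plausible but does not settle it. The opposite reading does not rescue the test. All three USPHS biological items have only grades A and B, so if B were acceptable, that domain could never fail on USPHS while it could on FDI.

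Item scores are recorded separately (Annex 2), so the item behind a domain difference would be visible afterwards. That is true, but without a prespecified map the explanation would be post hoc.

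A reader might infer that all three domains are mismatched, or that a rejection must be an artefact. The documents support neither: the Functional items pair, and at an assumed 5% bleeding rate with 10 shared failures Pearson gives p = 0.058. A reader might also take the Class II wording of the bleeding item as evidence for this point. Section 2.2 restricts the trial to vestibular cervical lesions, so the phrase is a clerical slip and carries no statistical weight.

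**Conclusion.** The point holds for the Esthetic and Biological domains only. There, a difference in acceptance at 24 months cannot separate disagreement about a shared feature from a difference in coverage, and the plan does not say which it means to test. Under the stated assumptions (one failed item fails the domain, a bleeding B is unacceptable, full agreement and no failures on shared items), 4 of 210 restorations suffice for Pearson and 6 for exact McNemar. With failures on shared items, Pearson needs more. The p-values treat restorations as independent, although a participant may contribute up to six.

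The reach is limited to one of ten null hypotheses; no comparison between adhesives changes. The change should be made because it costs little and makes the result interpretable either way.

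**What to change.** In section 2.7:
- Prespecify a map of six matched items: surface staining, colour, retention/fracture, marginal adaptation, post-operative sensitivity and caries. Note where the FDI item also covers vitality, erosion/abfraction or fracture, and reconcile the two headings of FDI item 2.
- State the acceptability cut for each item on each scale.
- Base the last hypothesis on these items, using McNemar's test plus an agreement measure, since both scales rate the same restorations. Adjust for multiplicity across the six items.
- Keep the domain totals as a descriptive whole-instrument comparison, with the rule that turns items into domain acceptance written out. Report luster, marginal discoloration, tooth integrity and gingival bleeding separately.

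As a separate wording correction, replace the Class II phrase in Annex 4 with a reference to the study's cervical restoration.

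The cost is SAP text and one annex phrase; the item scores are already collected. The downside is six paired tests instead of three domain tests. If Bonferroni were chosen, the threshold would be 0.05/6 = 0.0083, and exact McNemar would need 8 discordant restorations all in one direction (2 × 0.5⁸ = 0.0078) instead of 6. The agreement measure would still describe smaller discrepancies.

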Multimode one-bottle universal adhesives have been developed recently to make the clinical procedure even more user-friendly. These systems can be used for both direct and indirect restorations (16) and provide the flexibility for the clinician to select and choose the adhesive use mode (ER or SE) according to the clinical and dental hard tissues conditions. From a marketing perspective MM adhesives are highly innovative products offering the clinician the liberty of adapting a single-bottle SE adhesive for use as ER mode or as selective enamel etching (SE-EE) adhesion mode without compromising its bonding effectiveness (17). Controversy remains on, if these versatile adhesives contain technological advances for overcoming challenges associated with previous generations of adhesives or adhesion modes, since the available data mainly is based on in vitro findings. The concept behind these adhesives is novel; hence, only few short/mean-term clinical (16,18-20) and, immediate ultra-morphological and bond strength studies (21-25) have been reported. Some laboratory findings revealed that performance of universal multimode adhesives was shown to be material-dependent (23). Despite being considered user-friendly, acidity adjustment of MM adhesive solutions and incorporation of new functional monomers to promote clinical performance stability over time were the main changes proposed to improve these materials. Perdigao and colleagues observed during 18th month the clinical performance of the MM adhesive, Scotchbond Universal Adhesive (3M ESPE, St Paul, MN, USA) in non-carious cervical lesions (NCCLs) and concluded that, restorations retention with this universal adhesive was not dependent on the bonding strategy. Differences between use modes were detected only for adhesive restorations marginal adaptation, by FDI criteria (World Dental Federation- clinical criteria for direct/indirect restorations evaluation), but not by the USPHS (United States Public Health Service) criteria (16). Controversy remains about the use of MMP inhibitors to control the degradation of dentin-resin interfaces (26). According to the adhesion-decalcification (A-D) concept aggressive demineralization of hard tissues by strong acids results in dissolution of apatite crystallites, decreasing the opportunity to establish chemical bonds between SE

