One week, before the Restorative procedure (1st appointment): Inform the patient (Written/Verbal- Anexx-1); Patient signature of informed consent; Fulfilment of the project clinical file (patient identification, general clinical summary, oral clinic examination, oral hygiene state; Annex 2); Dental prophylaxis with fluoride toothpaste and water with a nylon brush. Vitality tests (cold and hot) executed with spray *Endo cool* (ethyl chloride) and warm instrument; Pre-operative sensitivity evaluation by applying air for 10 seconds from a dental syringe placed 2 cm from the tooth surface (16); NCCLs cavities will be evaluated according to the degree (1, 2, 3, 4) of sclerotic dentin (32), cavity dimensions (H-height, W-width, and D-depth) in millimetres (mm) and geometry (evaluated by profile photograph, as Angles Acute (A), Severe (S), Obtuse (O) (16);

1st Appointment-Intervention: Initial intra-oral/cavity surface and tooth digital photography; Teeth anaesthesia with 3% mepivacaine (Scandinibsa, Sintra Business Park, Portugal); Operatory field isolation with cotton rolls and retraction floss (Ultradent)._All cavities cleaned with pumice and water in a rubber cup, followed by rinsing and drying. Selection composite colour by shade guide; Adhesive interventions according to G1 to G6 arms assignment. Adhesive systems will be used as SingleDose mode. Composite restorations (AdmiraFusion Universal nano-hybrid composite) with incremental filling technique (two increments maximum), light-cured (LED Unit) with an intensity of 1000mW/cm2, during 40 seconds. Restorations will be finished immediately with diamond disks (OptiDisc® medium 40μm; Kerr) and burns. Polishing performed with diamond-impregnated silicone polishers (Dimanto, Voco, CuxHaven) during 10 seconds._Intra-oral digital photography of the restoration.

2.6-CLINICAL RECALL

Baseline (30 days after restoration), 12th and 24th months Appointments

1 - Intra-oral digital photography of the NCCL restoration;

2- Pos-operative sensitivity evaluation by applying air for 10 seconds from a dental syringe placed 2 cm from the tooth surface (16);

3 – Clinical direct evaluation by 3 calibrated examiners according to FDI (33) (Annex 3) and USPHS (34) (Annex 4);

4°- Data register.

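### The tenth hypothesis covers FDI and USPHS evaluation outcomes in general, but the SAP compares the scales only on acceptance, so grading differences within the acceptable range cannot be detected

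*Combined protocol and SAP*

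**What the plan says.** Under Objectives and Hypothesis, the tenth null reads "H0 - FDI or USPHS criteria evaluation outcomes not differ for the same data, at 24th month follow-up". It names no particular outcome.

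Section 2.7 has one analysis of scale against scale: "Comparison of FDI and USPHS acceptance (success rate) criteria evaluation outcomes for Esthetic", and likewise for the functional and biological parameters, which "at 24th Month Follow-up, were compared using the chi-square test". The layout of the table is not given. The general threshold applies: "Differences will be considered to be significant at P<0.05".

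The other analyses that use both scales do not compare them. "The changes in parameters clinical performance (paired comparison analysis) by both, FDI and USPHS criteria will be assessed by McNemar or Wilcoxon tests" concerns change over time on each scale. The agreement statistics in section 2.4 are within and between examiners.

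Section 2.6 has each restoration graded on both scales at the same visit. Annex 3 gives FDI five grades per item and ends each table with an acceptable or not acceptable call. Annex 4 gives USPHS two to four grades per item.

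**The concern.** The hypothesis is wider than its test. Two scales can give the same acceptance rate and still grade many restorations differently, for example FDI 2 where USPHS gives Alfa. Acceptance turns all such pairs into agreement.

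The Introduction cites an 18-month study in which "Differences between use modes were detected only for adhesive restorations marginal adaptation, by FDI criteria" and not by USPHS. That is a finding on a single item. The SAP compares pass or fail by domain, which pools marginal adaptation with retention. A divergence on one item within the acceptable range would leave no trace.

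At stake is the reading of a non-significant result. It would be natural to report that the two scales do not differ, and this test cannot support that statement.

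**Working it through.** **Inputs from the documents.** Six arms of 35 give 6 × 35 = 210 restorations (section 2.8), which reproduces the plan's total. The level is 0.05, taken as two-sided. Section 2.8 also gives 80 cases for a McNemar comparison, without discordance rates, power or level, so it cannot be reproduced; it is not stated for this test. No expected acceptance rate is given.

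**Assumptions.** FDI grades 1 to 3 count as acceptable, as their wording suggests; section 2.7 states no cut-off. Acceptance is varied from 70% to 99%. Restorations are treated as independent. Simulations use 800 runs.

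**Step 1: one table by hand.** Let 90% of 210 be acceptable on both scales (189 accepted, 21 not), and let 20% of 210 = 42 be FDI 2 but Alfa.
- Acceptance: 189/210 against 189/210, so chi-square = 0 and p = 1.
- Best grade, exact McNemar: 42 disagreements one way and 0 the other, so p = 2 × 0.5^42, about 5 × 10^-13.

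**Step 2: simulation, acceptance identical on both scales.**

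| Share regraded one way | Chi-square on acceptance, at 70, 90, 95 and 99% | Exact McNemar on best grade |
|---|---|---|
| 5% | 0% rejected | about 95–97% rejected |
| 10%, 20%, 40% | 0% rejected | 100% rejected |

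The acceptance rate makes no difference. The loss comes from dichotomising.

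**Step 3: when acceptance itself differs.** For the unpaired chi-square, z = (p1 − p2) / √(2p̄(1 − p̄)/n). With n = 210 and 2 failures on one scale:
- 9 on the other: z = 0.0333/0.0156 = 2.14, p = 0.03.
- 8 on the other: z = 0.0286/0.0149 = 1.92, p = 0.055.

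So 7 extra failures are needed from 99% acceptance. The same calculation gives 11 from 95% and 14 from 90%. Real differences in acceptance can therefore be found.

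**Step 4: pairing.** Suppose each restoration accepted on one scale has a 5% chance of failing on the other only. At 99%, 95% and 90% acceptance the chi-square rejects in 91%, 41% and 12% of runs; exact McNemar rejects in 95%, 93% and 90%. The unpaired test counts failures shared by both scales as noise.

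**Step 5: the other possible layout.** If chi-square is run on the FDI-by-USPHS cross-table, it tests association. With identical acceptance calls at 99% it rejects whenever at least one failure occurs: 1 − 0.99^210 = 0.88. At 95% or below it rejected in every run. Significance would then reflect agreement, the reverse of what the hypothesis needs.

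**The case against.** **Acceptance is a fair common metric.** Section 2.6 defines the study variable in terms of acceptance on both scales, and section 2.7 echoes the wording of the hypothesis, so the SAP can be read as its operational definition. Acceptance is also a natural way to put a five-grade scale beside one with two to four. This stands as a reason to keep the acceptance comparison. It does not license a conclusion wider than acceptance.

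**The scales can split on acceptance.** Partial loss is FDI grade 5 but USPHS Bravo. Low, transient sensitivity is FDI grade 2, while any sensitivity is USPHS B, which Annex 4 ties to pathology. Gingival bleeding is a USPHS item with no FDI counterpart. These could produce sizeable gaps, most plausibly in the biological domain. This stands in full. A reader might infer from the coarse endpoint that the null is bound to be retained; the annexes do not support that.

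**The ceiling.** A reader might also infer that acceptance will be close to 100% and that this is what disables the test. The documents give no acceptance rate; the Introduction says only that retention at two to three years was favourable. For a fixed one-way gap the chi-square gains power towards the ceiling (step 4: 12% from 90%, 91% from 99%). High acceptance matters only in so far as it keeps the gap small. With 180 restorations and the more lenient scale accepting 97% to 99% (both assumed), power for a 3-point gap is 14% to 41%.

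**Best grade is not a neutral comparator.** FDI 4.1 excludes cracks, while Alfa for retention asks only that the restoration is retained. FDI 5.1 also excludes discoloration. FDI 7.2 downgrades for erosion or abfraction, while USPHS asks only about caries. Some differences would thus follow from the definitions. This stands, and is why best grade should not replace acceptance as the sole basis for judging the hypothesis.

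**The cited study.** It found a difference between use modes by one scale, and the protocol does not tie it to the tenth null. It shows that scales can diverge on an item, and no more.

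**Conclusion.** The concern holds as a mismatch between hypothesis and test. A comparison of acceptance rates has no power against grading differences within the acceptable range, at any acceptance rate. A non-significant result would not show that FDI and USPHS agree. Differences in acceptance may still be found: about 7 to 14 extra failures in 210 suffice from 99% to 90% acceptance, if the chi-square compares two rates. The documents support neither a claim that acceptance is near its ceiling nor one that the null will be retained.

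The 0% in step 2 follows from the definition of acceptance. The 95% to 100% rests on assumed one-way regrading, all 210 restorations being observed, and independence. Section 2.2 allows up to six teeth per participant, so the real information may be less. One of ten hypotheses is affected; the comparisons between adhesives are not.

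**What to change.** Keep the acceptance comparison for the three domains, state which grades count as acceptable on each scale, and analyse it as paired data with McNemar on the same restorations.

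Add an item-level analysis for the six criteria that both scales contain: surface staining, colour, retention, marginal adaptation, sensitivity and caries. For each, give the full FDI-by-USPHS cross-table and a within-restoration comparison of the share in the best grade (FDI 1 against Alfa or A). Note beside each item where the best-grade definitions differ.

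Allow for several teeth per participant, for example with a cluster-adjusted McNemar test or a marginal model with participant as the cluster. Correct for the six items. Under Bonferroni the level is 0.05/6 = 0.0083, and ignoring clustering an exact test needs eight one-way disagreements (2 × 0.5^8 = 0.0078) instead of six (2 × 0.5^6 = 0.031).

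The alternative is to limit the tenth hypothesis, and whatever is concluded from it, to acceptance.

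The cost is SAP wording and some tables from data already on the Annex 2 forms. The downside is six item-level comparisons in addition to the three domain tests.
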